2.0 EPA PILOT STUDY ADD-ON OVERVIEW AND OBJECTIVES

2.1 Overview

This EPA pilot study will be conducted in homes recruited to participate in the Green Housing Study at the third study site (New Orleans). The Green Housing Study is a pre/post renovation study where participants participate for one month prior to renovation, the time required for renovation of their home, and 12 months post-renovation. The third study site location will be determined by CDC. In the third study site, 32 green intervention homes and 32 comparison homes will be included. Both the green-renovated and comparison homes will be from the same housing development or neighborhood to ensure homogeneity with regard to housing type and other socioeconomic factors. Changes in environmental measurements (pesticides, VOCs, particulate matter [PM_{2.5}], indoor allergens, fungi) over the 1-year follow-up period will be compared, thus each home's follow-up measurements will be compared with its own baseline measurements. In total, the EPA pilot study add-on will include approximately 12 months of data collection.

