Appendix C (The IRB-approved Protocol)

2.3 Sample Size Considerations

The sample size for the EPA pilot study add-on is fixed and dependent on CDC's grantee's ability to recruit and retain participants. Using available chemical concentration data for limonene (Sarigiannis et al., 2011), we can estimate the effect sizes we can see given various sample sizes (assumptions: design effect = 2.0, statistical power = 0.8, alpha level = 0.05, correlation = 0.3).

Example: Limonene in air ($\mu\text{g}/\text{m}^3$)

If non-renovated homes have a mean concentration and standard deviation = $15.0 \pm 19.4 \mu\text{g}/\text{m}^3$, with a fixed sample size of $n=35$ participants in each group (renovated and non-renovated homes), we could see a minimum size difference of $11.9 \mu\text{g}/\text{m}^3$.

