Appendix C (The IRB-approved Protocol)

5.0 DATA ANALYSIS PLAN

Our analysis approach will enable us to evaluate the objectives described in Section 2.0. Study participants will be characterized with regard to demographic variables such as age and gender as well as activity-related metrics from questionnaires and electronic devices. Housing and product information will be characterized based on questionnaire responses and technician information collection. Statistical analyses will be completed for target analytes and survey information at each study time point, as well as comparisons between time points and renovated/non-renovated homes. All media will be analyzed and compared between and among each media type. Cross-sectional, longitudinal, and pre/post renovation analyses will be conducted. Data quality (e.g., percent completion or detected, accuracy, precision) will be assessed to help make decisions on more complex statistical analyses that can be conducted with the available data.

Descriptive statistics, univariate analyses, and correlations will be employed to evaluate the pilot study data collected in the third study site. Descriptive statistics will be developed for all variables to be used in data analyses addressing the research objectives. Categorical variables will be summarized by frequencies, while continuous variables will be summarized by mean, standard deviation, median, and range. Environmental and biological measurement variables such as analyte concentrations in dust and urinary biomarker concentrations will be characterized by mean and standard deviation, median, range, appropriate distribution percentile values, and percent of measurements above the detection limit.

For detection limit censored data distributions, appropriate approaches for reducing bias in distributional parameter estimates will be considered (substitution, maximum-likelihood estimation, or beta-substitution, depending on the degree of censoring and sample sizes). Measurement distributions will be assessed for normality using the Shapiro-Wilks or other appropriate normality test. Depending on the distribution, measurement values may be log-transformed to compute geometric means and geometric standard deviations. Other types of transformations and/or non-parametric analysis methods will be considered if necessary.

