Appendix C (The IRB-approved Protocol)

Table 8. Summary of the data analysis plan

Objective	Measurements Required	Proposed Analysis Approach

1) Identify and characterize factors affecting children’s exposures to chemical ingredients from consumer products found in their everyday environment in order to support the data and modeling needs of the exposure components of EPA’s national research programs
	
Hand wipe, socks, house dust, air, soil, urine, blood measurements for target analytes; questionnaire and activity data
	
Descriptive and summary univariate statistics for measurement and survey data; correlation analyses within and between all collected data; geometric mean and standard deviation for target analytes to conduct t-tests of differences between sibling age groups; regression model analysis with target analyte measurements as outcome variables and product, activity, location, and housing variables as potential exposure factors

2) Evaluate the pilot study data metrics for incorporation in and enhancement of CDC’s ability to understand the relationship between environmental exposures and asthma in green versus traditional low-income housing
	
Survey responses from questionnaire; GPS; accelerometer data; housing data; multimedia measurement concentrations; QA/QC data for measurements and data collection; CDC measurement data
	
Data quality analyses such as precision, accuracy, range, % completion rate, % measureable, acceptability, compliance; descriptive statistics for measurement data; descriptive statistics for survey questions; correlations between survey responses on activity information and electronic information (GPS, accelerometer); correlations between EPA pilot study and CDC measurement data; assessment of impact of inclusion of EPA pilot study data in CDC asthma outcome models

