Appendix C (The IRB-approved Protocol)

Objective	Measurements Required	Proposed Analysis Approach

3) Compare multimedia measurements and survey data between pre- and post-renovation time points in green and traditional low-income housing to assess exposure-related changes in the residence and participants due to renovation activities
	
Chemical concentrations in available media (all chemicals, all media); mold information; activity information; all time points of data available for renovated and non-renovated homes; pre- and post-renovation information
	
Descriptive statistics; univariate statistics to compare chemical concentrations and mold at each time point and across renovated and non-renovated homes; correlations amongst chemicals and media; geometric mean and standard deviation for consumer product analytes in personal, residential, and biological samples by pre- and post-renovation time points; t-tests of differences between pre- and post-renovation time points; t-tests between siblings and pre- and post-renovation time points; non-parametric analysis of survey and activity response differences across time points and between renovated/non-renovated housing

4) Evaluate exposure to chemicals in household cleaning and personal care products as a modifying factor in interpreting the effectiveness of green housing renovations on reducing the incidence of asthma-like symptoms
	
Number of asthma-like symptoms reported by each participant; renovation status; total dust loading/air concentrations of measured cleaning product ingredients
	
Multiple regression models to examine the association between the primary risk factor (renovation status) and the outcome (symptom incidence) before and after including possible modifying factors (chemical concentrations). If inclusion of the additional variable causes the association between the primary risk factor and the outcome to change by 10% or more, then the additional variable is a potential effect modifier. Care will also be taken to assess any contributions to the outcomes of interest that are due to changes in medication and exposure-related behaviors rather than renovation.

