Appendix C (The IRB-approved Protocol)

Objective 2: Evaluate the pilot study data metrics for incorporation in and enhancement of CDC's ability to understand the relationship between environmental exposures and asthma in green versus traditional low-income housing

There are two elements for addressing Objective 2. First, the quality and suitability of measurement and survey data collected using the pilot study protocol will be evaluated. Second, for metrics found to be of adequate quality and suitability, EPA proposes to work with CDC to explore how incorporation of the additional exposure data may enhance the understanding of relationships between environmental exposures and asthma in renovated and traditional housing in the Green Housing Study.

Environmental, personal, and biological measurement data quality will be assessed by examining several factors including completeness, precision, accuracy, and percent measurable. Quality assurance objective criteria have been set for several factors: completeness (90%), precision ($\pm 25\%$), and recovery (70 – 130%). Ideally, for a given analyte, the percentage of samples with analysis results greater than the limit of detection (or method limit of detection) will be $>50\%$ to facilitate estimation of relevant distributional parameters and to support data analyses including assessment of differences between groups, correlations, and linear regression modeling. Descriptive statistics for the measurement data will be used to document concentrations of target analytes found in the indoor environment. Comparisons to measurement data collected in other observational human exposure measurement studies will be completed.

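### Objective 1 feeds geometric means and SDs estimated from non-detect data into t-tests: near 50% non-detects, two of the three listed methods reject about 10-12% at a nominal 5%, and the third shrinks a real fall

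*Protocol*

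**What the plan says.** The opening text of section 5.0 says that approaches to reduce bias in distribution parameters will be considered for data censored at the detection limit, and lists the candidates as "substitution, maximum-likelihood estimation, or beta-substitution, depending on the degree of censoring and sample sizes". It gives no cut-off, no substitution constant and no unit (group, analyte or medium) for making the choice. Non-parametric methods remain available if needed.

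Table 8 carries the summaries into tests. For Objective 1 the link is explicit: "geometric mean and standard deviation for target analytes to conduct t-tests of differences between sibling age groups". The narrative for Objective 1 lists geometric means and geometric SDs by sibling and age group, followed by t-tests and/or F-tests across those groups. For Objective 3, Table 8 lists "geometric mean and standard deviation for consumer product analytes in personal, residential, and biological samples by pre- and post-renovation time points" and then, as a separate item, t-tests between pre- and post-renovation time points.

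The narrative for Objective 2 sets an ideal, per analyte, for "the percentage of samples with analysis results greater than the limit of detection": above 50%, partly to support comparisons between groups. It is a target, not a condition for testing.

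**The concern.** Maximum likelihood and beta-substitution can estimate a log-scale mean and SD well when some values are censored. But the standard error of that mean is larger than SD/√n, because a non-detect carries less information than a measured value. An ordinary t-test built from the estimates and the full n uses SD/√n and so overstates the precision.

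Substitution has the opposite weakness. It behaves like complete data under the null, but it pins every low value to one constant, so a real fall in concentration is partly hidden. Section 1.2 of the protocol hypothesises lower contaminant levels in green homes, so unequal censoring between the compared sets is what the study expects.

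Objective 1 relies directly on these tests for many trace analytes. Objective 3 also uses t-tests on the same kind of data. At stake are false differences under two of the listed methods and understated renovation effects under the third.

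**Working it through.** **The plan's own figure.** The add-on states no error rate for non-detect handling. Its one computed figure is a detectable limonene difference of 11.9 µg/m³ (section 2.3: "design effect = 2.0, statistical power = 0.8, alpha level = 0.05, correlation = 0.3", SD 19.4, 35 per group). It reproduces as (1.645 + 0.842) × 19.4 × √[2 × 2.0 × (1 + 2 × 0.3)/(3 × 35)] = 11.91, that is, one-sided with three repeated measures. Section 2.3 states neither; that is a separate matter. What is used here is the spread: mean 15.0 and SD 19.4, if log-normal, imply GSD = exp{√ln[1 + (19.4/15.0)²]} = 2.70.

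**Other inputs.** 32 homes per group (section 2.1: "32 green intervention homes and 32 comparison homes will be included") or 35 (section 2.3). Assumed: log-normal data, one detection limit (LOD), independent groups.

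**1. Maximum likelihood in both groups, no true difference.** Let p be the share of non-detects, a = Φ⁻¹(p), f = φ(a), g = f/p. The large-sample information per observation, in units of the log SD, is:
- I11 = 1 − p + f(g + a)
- I12 = f[1 + a(a + g)]
- I22 = 2(1 − p) + a·f[1 + a(a + g)]

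The variance of the estimated mean relative to SD²/n is V = I22/(I11·I22 − I12²). A nominal 5% test that ignores V rejects with probability 2[1 − Φ(1.96/√V)].

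At p = 0.50: a = 0, f = 0.399, g = 0.798, so I11 = 0.818, I12 = 0.399, I22 = 1. Then V = 1/(0.818 − 0.159) = 1.52, and rejection is 2[1 − Φ(1.59)] = 11.2%. The same formula gives:
- p = 0.30: V = 1.14, 6.6%
- p = 0.35: V = 1.20, 7.3%
- p = 0.65: V = 2.40, 20.6%

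Simulation agrees. Maximum likelihood gives about 6-7% at 35%, 10-12% at 50% and 20% at 65%. In 20,000 replicates at GSD 2.7 and 50% non-detects, maximum likelihood gave 10.6-11.1% and beta-substitution 11.9-12.3%. The protocol gives no beta-substitution formula, so the usual form was assumed. Choosing a single method on the pooled censoring, but keeping the t-test, gave 7.1-11.8%. At 30% non-detects every rule tried (GSD 2-4) gave 4.6-7.2%.

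**2. Substitution in both groups.** Under the null at 50% non-detects the t-test holds 5.0-5.3%. For a true halving, take GSD 3 (log SD s = 1.099) and 35% non-detects before. Set the earlier log mean to 0, so the log LOD is c = −0.385 × 1.099 = −0.423. Afterwards the log mean is −0.693, a = (−0.423 + 0.693)/1.099 = 0.246, and non-detects are 60%. With k the substitution divisor, the mean of the substituted logs is p(c − ln k) + (1 − p)μ + s·φ(a).
- LOD/√2: 0.137 before, −0.314 after; ratio exp(−0.451) = 0.64.
- LOD/2: 0.016 before, −0.521 after; ratio exp(−0.537) = 0.58.

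The true ratio is 0.50.

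**3. Different methods in the two groups.** This needs an assumed rule. With a switch at 50% non-detects within each group, at GSD 2.7 and 50% non-detects:
- LOD/√2 below the cut: 28-29% with maximum likelihood above it, 31-32% with beta-substitution above it.
- LOD/2 below the cut: 10-13%.
- Maximum likelihood below the cut: about 6% with LOD/2 above it, about 1% with LOD/√2 above it.

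**4. Tests that respect censoring.** At 50% non-detects a censored-likelihood ratio test of mean and SD together gave 5.3-5.7%, and a rank-sum test with non-detects tied gave 4.3-5.0%.

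**The case against.** The strongest reply is that the plan commits to very little. Approaches are only to be considered, and the algorithm, cut-off and constant are details that a separate statistical analysis plan may settle. The narrative for Objective 1 first screens for variables with enough measurable results and allows non-parametric tests, section 5.0 uses percent detected to decide on more complex analyses, and the detection target puts 50% non-detects at the edge of what is intended and 65% beyond it. Only the Objective 1 cell of Table 8 ties geometric mean and SD to t-tests; in the Objective 3 cell they are separate items. The compared sets are often siblings or the same home over time, which the calculations treat as independent.

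Much of this stands. The explicit link is confined to Objective 1, the inflation is small at 30-35% non-detects, and the rates do not transfer directly to paired contrasts. What remains is more than missing detail. The detection target is only an ideal. The non-parametric option is raised in connection with distribution shape and survey or activity categories, not censoring. And none of the three listed methods, followed by a t-test, gives both a valid error rate and an undistorted contrast under heavy censoring.

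A reader might also infer that each compared group gets its own method according to its own censoring, and so quote a false-positive rate near 30%. The documents do not support that. Section 5.0 names no group-level choice, and where the protocol gives a unit for the detection rate, it is the analyte. The high figure also depends on an assumed cut-off, constant and order of methods.

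**Conclusion.** The concern holds in a limited form. For Objective 1, following maximum likelihood or beta-substitution with a full-n t-test makes a nominal 5% test reject about 10-12% at 50% non-detects, and about 20% at 65% with maximum likelihood, even with the same method in both groups. At 30-35% the rate is about 5-7%. Substitution holds about 5% but turns a true ratio of 0.50 into about 0.58-0.64 when non-detects rise from 35% to 60%. The attenuation would also affect Objective 3 if substitution were used there.

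Different methods in the two groups are neither prescribed nor barred. If they occurred, the error could reach about 28-32% under one assumed rule, and could fall below 5% under another.

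All error rates rest on independent log-normal groups, a common LOD and 32-35 per group. The attenuation figures assume GSD 3.

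**What to change.** In section 5.0 and Table 8:

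- Use one non-detect method per analyte and medium, the same for every group and visit.
- Do not run t-tests on geometric means and SDs estimated from censored data; keep those summaries for description.
- Compare groups and visits by censored (Tobit) regression on log concentration, with a home-level random effect or home-clustered inference for repeated visits and siblings. Take the geometric mean ratio and its interval from that fit.
- Where pooled detection is under 50%, compare detection rates, or use a rank test with all values below the highest LOD tied. Respect the pairing of siblings and visits in either case.

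The home-level term is needed. With four visits and the protocol's correlation of 0.3, ignoring it inflates the variance of a group effect by 1 + 3 × 0.3 = 1.9. On an uncensored approximation, a nominal 5% test would then reject 2[1 − Φ(1.96/√1.9)], about 15%.

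The cost is plan wording and a standard model. The downside is wider intervals for heavily censored analytes. The calculations above did not test the model on clustered data, so its error rate should be checked by simulation at the planned sample size.

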Appendix C (The IRB-approved Protocol)

Table 8. Summary of the data analysis plan

Objective	Measurements Required	Proposed Analysis Approach

1) Identify and characterize factors affecting children’s exposures to chemical ingredients from consumer products found in their everyday environment in order to support the data and modeling needs of the exposure components of EPA’s national research programs
	
Hand wipe, socks, house dust, air, soil, urine, blood measurements for target analytes; questionnaire and activity data
	
Descriptive and summary univariate statistics for measurement and survey data; correlation analyses within and between all collected data; geometric mean and standard deviation for target analytes to conduct t-tests of differences between sibling age groups; regression model analysis with target analyte measurements as outcome variables and product, activity, location, and housing variables as potential exposure factors

2) Evaluate the pilot study data metrics for incorporation in and enhancement of CDC’s ability to understand the relationship between environmental exposures and asthma in green versus traditional low-income housing
	
Survey responses from questionnaire; GPS; accelerometer data; housing data; multimedia measurement concentrations; QA/QC data for measurements and data collection; CDC measurement data
	
Data quality analyses such as precision, accuracy, range, % completion rate, % measureable, acceptability, compliance; descriptive statistics for measurement data; descriptive statistics for survey questions; correlations between survey responses on activity information and electronic information (GPS, accelerometer); correlations between EPA pilot study and CDC measurement data; assessment of impact of inclusion of EPA pilot study data in CDC asthma outcome models

Appendix C (The IRB-approved Protocol)

Objective	Measurements Required	Proposed Analysis Approach

3) Compare multimedia measurements and survey data between pre- and post-renovation time points in green and traditional low-income housing to assess exposure-related changes in the residence and participants due to renovation activities
	
Chemical concentrations in available media (all chemicals, all media); mold information; activity information; all time points of data available for renovated and non-renovated homes; pre- and post-renovation information
	
Descriptive statistics; univariate statistics to compare chemical concentrations and mold at each time point and across renovated and non-renovated homes; correlations amongst chemicals and media; geometric mean and standard deviation for consumer product analytes in personal, residential, and biological samples by pre- and post-renovation time points; t-tests of differences between pre- and post-renovation time points; t-tests between siblings and pre- and post-renovation time points; non-parametric analysis of survey and activity response differences across time points and between renovated/non-renovated housing

4) Evaluate exposure to chemicals in household cleaning and personal care products as a modifying factor in interpreting the effectiveness of green housing renovations on reducing the incidence of asthma-like symptoms
	
Number of asthma-like symptoms reported by each participant; renovation status; total dust loading/air concentrations of measured cleaning product ingredients
	
Multiple regression models to examine the association between the primary risk factor (renovation status) and the outcome (symptom incidence) before and after including possible modifying factors (chemical concentrations). If inclusion of the additional variable causes the association between the primary risk factor and the outcome to change by 10% or more, then the additional variable is a potential effect modifier. Care will also be taken to assess any contributions to the outcomes of interest that are due to changes in medication and exposure-related behaviors rather than renovation.

Appendix C (The IRB-approved Protocol)

Objective	Measurements Required	Proposed Analysis Approach

5) Examine the relationships between consumer products in a residence, environmental concentrations, and exposure to active ingredients found in consumer product chemicals to support development and evaluation of models for predicting exposure to these chemicals
	
Household consumer product inventories, house dust, surface wipes, air, blood, urine concentrations
	
Quantification of relationships among media (dust, wipes, air) concentrations by chemical (correlations within and between subjects, descriptive statistics of ratio of air concentrations to surface concentrations); correlation between media (air and dust) concentrations and biomarker concentrations (within and between subjects by chemical); comparison of chemicals (individual or by class) in products found in the home with those found in dust and air (presence/absence) based on available databases of chemical ingredients; comparison of chemicals (individual or by class) in product categories reported as used in the home with those found in media (presence/absence, correlation of magnitude with reported use frequencies) based on available databases of chemical ingredients

6) Measure biomarkers of consumer product chemicals for young children in conjunction with environmental measurements to evaluate exposure and dose models
	
House dust, air, duplicate diet, blood, urine concentrations; activity information; survey information
	
Descriptive statistics; correlation analyses; uni- and multi-variate analyses for biomarker measurements; model runs (e.g., SHEDS, PBPK model, PROCEED) for forward/reverse dosimetry; comparison (t-test, correlations) between measurements and model predictions

7) Assess rapid, low burden, low cost methods for characterizing consumer product use in the residential environment to predict exposure to chemicals
	
Photographs of storage locations for household cleaning products and personal care products; barcode scanner inventory of products
	
EPA investigators will identify products in the photographs (blinded to scanner inventory). Image-based inventories will be evaluated against barcode-based inventories to assess collection accuracy (number of products correctly identified in photo divided by number in scanned inventory)

